4. AAT and measurements of the same data will continue up to three times weekly after the initial measurements and will be listed on data collection sheets. If the patient is unavailable for AAT at the time of the scheduled intervention, the research team will document "unavailable," indicate the reason for unavailability. The patient will remain in the study and data collection will continue until the patient is discharged, reaches RLAS 7, or have been hospitalized ≥ 28 days. If the patient has been discharged from the study but remains in the hospital, he/she may continue to receive AAT.

Control Group

1. When the patient is randomized to the control arm, data measurements will be taken by the bedside RN. Variables to be collected include:
 - A. RLAS Score
 - B. GCS Score
 - C. Level of Command-0, 1 or 2 or 3-step (see same data collection sheet).
 - D. Movement of Extremities
2. The control group will be receiving standard of care bedside interventions. During the control measurement period, the only person present will be the bedside nurse who records the measurements. RLAS, GCS, and Level of Command and movement of extremities will be measured by the same licensed healthcare professional before and after each interaction with the healthcare professional.
3. The PI will be responsible for collecting measurements of the same data up to three times weekly after the initial measurements until they are discharged, reach RLAS 7, or have been hospitalized ≥ 28 days.

When the subject is moved to a different unit, study personnel will continue to be responsible for ensuring the study measurements, as measured by the bedside nurse, are recorded on the data collection form.

Methods for Tracking Recruitment and Retention. Study personnel will:

- Screen the trauma services database to determine the number of patients appropriate for the study.
- Keep detailed notes regarding the number of patients identified as potential participants by the study personnel to determine the percentage of eligible patients approached for inclusion into the study to determine the efficacy of our program to treat this population

- Keep detailed logs reflecting the number of patients approached to participate and the reasons for declining participation and for loss to follow up to determine the willingness of participants to consent to participate and remain in the study.

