3.4. Endpoints/Outcome Measures

Patients enrolled in the study will participate until any of the following occurs:

1. choose to no longer participate
2. develop animal allergies
3. reach a RLAS of 7 or above
4. are discharged
5. are hospitalized for greater than or equal to 28 days.

3.5. Consent/Assent: Informed consent will be obtained by the PI or TICU RNs who are sub-investigators on the study. Patients or legally authorized representative of potential subjects will give consent. Patients who do not speak English or Spanish will not be consented.

3.6. Monitoring Subjects and Criteria for Withdrawal of Subjects from the Study.

Criteria for withdrawing subjects from the study are at patient and/or patient LAR request.

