4.2. Method of Data Analysis

Aim 1: To determine if the use of animal assisted therapy in the plan of treatment of patients with TBI results in higher scores on the Ranchos Los Amigos, Glasgow Coma Scale, an increased ability to follow commands, and an increased movement of extremities than those who do not receive AAT.

The difference in RLAS scores from pre-intervention to post the intervention will be the primary outcome for the analysis. The outcome, Δ RLAS, will be defined as RLAS during AAT/sham – RLAS pre-AAT/sham. Δ RLAS from each study visit (AAT or sham) will be averaged over each week of the study (weeks 1-4). To address the primary hypothesis, weekly Δ RLAS will be compared between the AAT group and controls using nonparametric Wilcoxon rank sum tests (Mann-Whitney U tests) in order to determine whether the AAT group has significantly higher Δ RLAS. This analysis will be stratified by weeks 1-4 to determine whether the difference in Δ RLAS between AAT and controls changes over time.

The difference in LOCmd scores and movement of extremities will be a secondary outcome of this study. Δ LOCmds and movement of extremities will be defined similarly to Δ RLAS, as the LOCmds and movement of extremities during AAT/sham – LOCmds and movement of extremities pre-AAT/sham, and the mean Δ LOCmds and movement of extremities will be calculated for each week of the intervention (1-4). Weekly

Δ LOCmd scores and movement of extremities will be compared between study groups (AAT vs. controls) using nonparametric Wilcoxon rank sum tests. This analysis will be stratified by weeks 1-4 to determine whether the difference in Δ LOCmd and movement of extremities between AAT and controls changes over time.

GCS scores are routinely collected every hour by the TICU nursing staff. Medical charts will be reviewed to record the GCS scores during the hour immediately before and immediately after the intervention (or sham) is implemented. Δ GCS will be defined as GCS after AAT/sham – GCS pre-AAT/sham. Weekly Δ GCS scores will be compared between study groups (AAT vs. controls) using nonparametric Wilcoxon rank sum tests. This analysis will be stratified by weeks 1-4 to determine whether the difference in Δ GCS between AAT and controls changes over time.

Aim 2: To determine if the use of animal assisted therapy in the plan of treatment of patients with TBI are discharged with a higher degree of cognitive function than those who did not receive AAT.

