To address the primary hypothesis, weekly Δ RLAS will be compared between the AAT group and controls using nonparametric Wilcoxon rank sum tests (Mann-Whitney U tests) in order to determine whether the AAT group has significantly higher Δ RLAS. This analysis will be stratified by weeks 1-4 to determine whether the difference in Δ RLAS between AAT and controls changes over time.

The difference in LOCmd scores will be a secondary outcome of this study. Δ LOCmd and movement in extremities will be defined similarly to Δ RLAS, as the LOCmds and movement of extremities during AAT/sham – LOCmds and movement of extremities pre-AAT/sham, and the mean Δ LOCmds and movement of extremities will be calculated for each week of the intervention (1-4). Weekly Δ LOCmd scores and movement of extremities will be compared between study groups (AAT vs. controls) using nonparametric Wilcoxon rank sum tests. This analysis will be stratified by weeks 1-4 to determine whether the difference in Δ LOCmds and movement of extremities between AAT and controls changes over time.

4.3. Data Storage: The data will be stored on a password protected computer in the AAC office for three years in a Microsoft Excel 2010 database and then destroyed. Only study personnel will have access to these data.

4.3.1. Data Management: Information about study subjects will be kept confidential and managed according to the requirements of the Health Insurance Portability and Accountability Act of 1996 (HIPAA). Privacy and confidentiality of all enrolled patients will be maintained. All data collection tools will be taken to the AAC Office and will be entered by LH into the secure study data base. Consent documents and the regulatory binder will be kept in the Trauma Research Manager's office. The Trauma Department suite is locked, and the Trauma Research Manager's office is locked.

4.3.2. Records Retention: The data will be stored for three years in a Microsoft Excel 2010 database and then destroyed.

5. HUMAN SUBJECTS PROTECTION (RISKS, BENEFITS, and ALTERNATIVES)

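### The separate weekly Wilcoxon tests in Section 4.2 cannot determine whether the AAT-control difference changes over time: no test compares weeks, and later weeks contain only the patients still under measurement

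*Protocol*

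**What the plan says.** Section 3 (Study Methods and Procedures) sets the same end of measurement in both arms. Intervention Group item 4 reads "The patient will remain in the study and data collection will continue until the patient is discharged, reaches RLAS 7, or have been hospitalized" for at least 28 days. Control Group item 3 reads "until they are discharged, reach RLAS 7, or have been hospitalized", with the same limit. Section 3.4 repeats the rules: patients take part until they "reach a RLAS of 7 or above", are discharged, or "are hospitalized for greater than or equal to 28 days", among other reasons. RLAS is also the scale of the primary outcome. The paragraph of Section 3 just before 3.3 expects that mortality may require the sample size to be adjusted.

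Section 4.2 takes the change in RLAS within each session. These changes "will be averaged over each week of the study (weeks 1-4"), and the arms are compared week by week with Wilcoxon rank sum tests "in order to determine whether the AAT group has significantly higher" change. It then adds: "This analysis will be stratified by weeks 1-4 to determine whether the difference in" the change in "RLAS between AAT and controls changes over time". Similar sentences follow for level of commands, movement of extremities and GCS. The RLAS and level-of-commands sentences recur under Aim 2, and the RLAS sentence is also in the abstract.

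Hypothesis 1 (Section 1.2) expects faster recovery on RLAS under AAT.

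**The concern.** The plan names a conclusion (the effect does or does not change over four weeks) and a method that cannot deliver it. Two separate things are wrong.

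First, a set of within-week tests contains no comparison between weeks. A significant week 1 and a non-significant week 4 is not evidence that the two differences differ. This would hold even if nobody left.

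Second, the patients change from week to week. One exit rule is a level on the outcome scale itself. Discharge and death also depend on the patient's course, and they remove patients from opposite ends of prognosis. The week 4 groups are therefore defined after randomisation. If AAT speeds recovery, as Hypothesis 1 expects, they may be selected differently in the two arms.

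At stake is the reading of a weekly pattern on the primary outcome: an apparent fading or growth of the effect could come from who is left, or from smaller groups.

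**Working it through.** **1. What the weekly tests compare.** Let D_w be the AAT-control difference in mean session change among patients measured in week w. A statement about change over time concerns a contrast such as D_4 - D_1. Section 4.2 plans tests of D_1, D_2, D_3 and D_4 against zero, and no contrast between them.

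**2. Smaller groups alone.** Inputs: about 50 per arm (Section 4.1). The protocol gives no effect size, SD or attrition rate, so assume a constant standardised effect of 0.5, a two-sided 5% level and a two-sample comparison of means. Power is 0.705 at 50 per arm, and 0.609, 0.424 or 0.277 if 40, 25 or 15 per arm remain in week 4. Treating the weeks as independent, the chance of significance in week 1 but not in week 4 is power_1 × (1 - power_4):

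- 40 left: 0.705 × 0.391 = 0.28
- 25 left: 0.705 × 0.576 = 0.41
- 15 left: 0.705 × 0.723 = 0.51

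For effects of 0.4 to 0.6 the range is 0.20 to 0.53. Nothing changed over time in any of these cases.

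**3. Selection.** Let d_i be patient i's own session effect, constant over weeks, and S_iw = 1 if patient i is still measured in week w. Then

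E[d_i | S_iw = 1] = E[d_i] + Cov(d_i, S_iw) / P(S_iw = 1).

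The weekly difference drifts whenever response is related to staying under measurement. The protocol gives nothing from which to fix the sign of that covariance.

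**4. Size, by simulation.** Everything here except 50 per arm and the exit rules is assumed: start level uniform 2-4; natural rise lognormal with mean 0.12 levels per day and log SD 0.5; sessions on days 1, 3 and 5 of each week; each session raises RLAS by one level with probability 0.10 in control and 0.10 + d_i under AAT; d_i has SD 0 or 0.625 × its mean and correlation 0, ±0.3 or ±0.6 with the natural rate; 0, 25% or 50% of d_i is kept after each session; exit at level 7 or hospital day 28, plus other exits (1% per session at random, or level-linked); entry on hospital day 0 or spread over days 0-10.

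| True difference (constant) | Week 2 | Week 3 | Week 4 |
|---|---|---|---|
| 0.40 | 0.39-0.41 | 0.32-0.42 | 0.22-0.45 |
| 0.20 | 0.20-0.21 | 0.18-0.21 | 0.15-0.23 |
| 0.10 | not shown | not shown | 0.08-0.12 |

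The lowest week 4 ratio is 0.224/0.40 = 56% (correlation +0.6, half the gain kept). The highest are about 112-114%, for example 0.45/0.40 = 112%. At true 0.40, a correlation of -0.6 gives 0.44-0.45 with no gain kept but 0.32-0.33 with half kept, so even the direction turns on unknowns.

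These runs end measurement on the underlying level. If the score recorded at a session can itself trigger the RLAS 7 exit, a session that lifts a patient to 7 is that patient's last. Week 4 is then about 0.41-0.46 at true 0.40 even when the effect is equal in all patients (0.46/0.40 = 115%). A rerun of the whole grid under that reading reached 0.127 at true 0.10 (127%). Hence an upper end of about 115-130%, depending on the model.

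**5. Numbers left in week 4 at true 0.40 (first reading of the exit).** AAT 15-39 v control 36-39 with entry on day 0; 9-23 v 22-23 with entry over days 0-10. The 28 days run from hospitalisation and entry waits for GCS 5 (Section 2.7), so a first session on hospital day 7 leaves 28 - 7 = 21 days and no fourth study week, if weeks count from the first session. This thins week 4 but does not by itself make the arms unlike.

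**6. No effect.** With no AAT effect each weekly test rejected in 4-6% of trials.

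**The case against.** *The statistical analysis plan may deal with exits or add an arm-by-week model.* It may. But the protocol does not leave the matter open: it fixes the method and states the conclusion the method is to support. That sentence is wrong as it stands.

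*The size rests on stacked assumptions.* This stands. The 56% figure needs half of AAT sessions to gain a full level (0.10 + 0.40) against 10% of control sessions, half of that effect kept, and a strong link between response and recovery. The extra recovery would be 3 × 0.5 × 0.40 = 0.6 levels a week on a natural 7 × 0.12 = 0.84, or about 70% faster. At true 0.10 the distortion is at most about 0.02 levels, and if the session score triggers exit, the fall under correlation +0.6 nearly vanishes (0.096-0.099; entry on day 0, random exits). The figures show what is possible, not what to expect.

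*Much of the pattern is sample size.* This also stands. In the strongest selection case, significance in week 1 but not in week 4 arose in 20-52% of trials at true 0.40, against 0-16% at the same group sizes without selection; at 0.20, 32-68% v 16-52%; at 0.10, 43-51% v 36-49%. The protocol states no rule that reads change from such a pattern. Either cause still defeats the time-trend reading.

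*Stronger readings.* A reader might infer that the primary comparison is biased or its false-positive rate inflated. The null runs and weeks 1-2 do not support that, and the sign of the difference never reversed in the main grid. A reader might infer that the effect will appear to fade. The documents fix neither response heterogeneity nor carry-over, and the drift can go up as well as down. Nor may one say that an equal effect guarantees a flat weekly difference: that depends on what counts as reaching RLAS 7.

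**Conclusion.** The concern holds, as a minor point about a stated conclusion. The weekly tests cannot determine whether the effect changes, first because no weeks are compared, and second because the patients in weeks 3-4 are selected after randomisation, possibly differently by arm. Both reasons follow from the text of Sections 3, 3.4 and 4.2 without any assumed parameter. Only the size, about 56% to about 115-130% of a constant effect in week 4, rests on assumptions, and its direction cannot be known from the protocol. Whether AAT has the higher change in RLAS remains answerable as planned, so this defect does not require a different primary test.

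**What to change.** In 4.2 (RLAS, level of commands, movement of extremities, GCS, and the repeat under Aim 2) and in the abstract, replace the sentence about determining change over time with: *Weekly differences describe patients still under measurement in that week and are not used to conclude that the effect changes.* Report, by arm and week, the numbers contributing and the reasons for exit, including death. Section 3 already requires logs of unavailability and of loss to follow-up with reasons. The cost is wording and one table. The exit rules stay as they are, and the weekly results lose any claim to show a trend.

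Optional, and not required by this defect: base the primary Wilcoxon test on one value per patient, the mean session change in RLAS before exit. In the simulations it gave 0.40 at true 0.40 in every run, largely because personal effects were held constant. Its downside is some dependence on length of stay if the effect truly changes. With a true fade of 0.6, 0.4, 0.3, 0.2 it gave 0.40-0.44 when the arms left at equal rates and 0.43-0.47 when AAT patients left faster.

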1. INTRODUCTION

1.1 .Specific Aims

Aim 1: To determine if the use of animal assisted therapy in the plan of treatment of patients with TBI results in differences in scores on the Ranchos Los Amigos Scale, Glasgow Coma Scale, and in an increased ability to follow commands from those who do not receive AAT.

Aim 2: To determine if the use of animal assisted therapy in the plan of treatment of patients with TBI are discharged with a different degree of cognitive function than those who did not receive AAT.

1.2 .Hypothesis

Hypothesis 1 Patients sustaining TBI who participate in AAT will experience a faster and higher elevation in RLAS, GCS scales and the ability to follow commands than those TBI patients who do not receive AAT.

Hypothesis 2 Patients sustaining TBI who participate in AAT will experience a faster and higher elevation in cognitive function (as evidenced by the ability to follow multiple commands) than those TBI patients who do not receive AAT.

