1.3. Background and Significance

Patients who have sustained TBI can have significant decreases in their level of consciousness. This can interfere with the patients' abilities to (1) actively participate in their recovery and can inhibit their ability to breathe without artificial support, (2) obtain adequate nutritional input, and to (3) follow commands to increase range of motion and physical strength. Several of these patients have long intensive care unit and acute care lengths of stay.

The costs associated with the care of patients with TBI are quite high. In 1995, the total direct and indirect financial costs of patients with traumatic brain injuries were estimated at \$56 billion [1]. Schootman et al., estimate 254,500 TBIs required hospitalization in 1996 within the United States, with 5.4 billion US dollars charged to treat these injuries during acute hospitalization [2]. Patient age, increasing severity of injury and urban teaching hospitals were associated with higher charges. McGarry et al estimated the cost of hospitalization for moderate, serious, severe or critical TBI to be \$8,189, \$14,603, \$16,788 dollars, and \$33,537 respectively [3]. Costs also varied by injury type, averaging \$20,084 for gunshot wounds, \$20,522 for motor

vehicle crashes, \$15,860 dollars for falls, and \$19,949 for blows to the head. In this study we seek to demonstrate that the introduction of AAT can increase level of consciousness and cerebral function earlier and, therefore decrease cost of the provision of care to these patients.

Animal Assisted Care (AAC) is an ongoing and well-established program on the Inova Fairfax Medical campus. The main objective of the Animal Assisted Care Program is similar to the Pet Partner's[®] Program objective, which is to improve the patients' well-being through meeting some of their physical and emotional needs with the use of animals in the acute care environment^[4].

The AAC Program provides five modalities of therapeutic interventions (also known as animal assisted interventions (AAI):

1. **Animal Assisted Activities or Visitation**—the Pet Partner Team[®] Training Manual defines these as goal-directed activities designed to improve patients' quality of life through utilization of the human/animal bond. Animals and their handlers must be screened and trained. Activities may be therapeutic but are not guided by a credential therapist. ^[5]

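### Aim 2 asks about cognitive function at hospital discharge, but no score is scheduled at discharge and measurement ends earlier for patients who reach RLAS 7 or day 28 in hospital

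*Protocol*

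**What the plan says.** The Abstract and Section 1.1 put Aim 2 as whether patients given AAT "are discharged with a different degree of cognitive function than those who did not receive AAT". Section 4.2 restates it in one direction: "are discharged with a higher degree of cognitive function than those who did not receive AAT". Hypothesis 2 (Section 1.2) takes the following of multiple commands as the evidence of cognitive function.

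Section 3 sets the end of measurement. In the intervention group, "data collection will continue until the patient is discharged, reaches RLAS 7, or have been hospitalized ≥ 28 days". In the control group scores are collected "until they are discharged, reach RLAS 7, or have been hospitalized ≥ 28 days". Section 3.4 lists the ends of participation, among them "reach a RLAS of 7 or above" and "are hospitalized for greater than or equal to 28 days", with discharge as a separate item. Section 3 adds, for the intervention group: "If the patient has been discharged from the study but remains in the hospital, he/she may continue to receive AAT".

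Under Aim 2, Section 4.2 compares weekly averages of the change from before to during a session, in RLAS, level of commands (LOCmd) and movement of extremities, for weeks 1 to 4. The Statistical Methods in the Abstract also give Aim 2 a within-session change.

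**The concern.** A question about status at discharge needs a score at discharge, or at least one close to it. The protocol foresees patients who have left the study and are still in hospital, and Section 1.3 suggests that long stays are not rare: "Several of these patients have long intensive care unit and acute care lengths of stay". Those patients have no study score when they go home or move on.

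The gap is not random. One of the two early stops is triggered by the RLAS itself, which is also the leading outcome. If AAT works as Hypothesis 1 expects, patients in the AAT arm reach RLAS 7 sooner and stop being measured sooner, so the absent discharge scores may be distributed differently in the two arms. At stake is one of the trial's two stated aims. An analysis plan written later cannot repair this, because a score that was never taken cannot be recovered.

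**Working it through.** The plan gives no figure on this point, so the check sets the passages side by side.

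1. **What discharged means in Aim 2.** Section 3.4 lists discharge apart from the RLAS and 28-day stops, and Section 3 distinguishes leaving the study from leaving the hospital. The unqualified word in Aim 2 therefore reads as hospital discharge.
2. **When scoring ends.** In both arms it ends at the first of discharge, RLAS 7 and 28 days in hospital. Section 3.4 agrees and adds two further exits, the patient's choice and a new animal allergy.
3. **Who has a score at discharge.**
   - Patients who stop at RLAS 7 or day 28 and stay in hospital: none. Section 3 describes no later measurement.
   - Patients discharged before either stop: no discharge-day assessment is scheduled. Sessions take place up to three times a week, so the nearest value is the last session.
4. **Other sources.** Section 4.2 reviews the chart only for GCS, and only for the hours around a session. The protocol describes no source for RLAS and LOCmd other than study measurement. A GCS may be in the chart while the patient is in the TICU, but no review at discharge is planned.
5. **What is analysed under Aim 2.** Weekly within-session changes only. No discharge value and no last study value enters.

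Steps 3 and 5 are separate faults. The data for the aim are not collected, and the analysis listed under the aim addresses a different quantity.

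**Illustration of lost precision, on assumed inputs.** The protocol gives about 50 patients per group (Sections 2.4 and 4.1), without alpha, power or effect size. Assume two-sided alpha 0.05, power 80%, a normal approximation, and patients without a discharge score left out equally in both arms. The detectable difference in SD units is (1.960 + 0.842) × √(2/n).

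| Assumed share without a score | n per arm | Detectable difference | Power for 0.56 SD |
|---|---|---|---|
| 0% | 50 | 2.802 × 0.200 = 0.56 | 80% |
| 10% | 45 | 2.802 × 0.211 = 0.59 | 76% |
| 30% | 35 | 2.802 × 0.239 = 0.67 | 65% |
| 50% | 25 | 2.802 × 0.283 = 0.79 | 51% |

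The true share is not in the protocol. The table shows only how the loss would grow, and it leaves out any bias from unequal losses.

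**The case against.** The strongest reply is that the planned Aim 2 analysis uses no discharge score, so nothing in it is damaged by the stops, and that the fault is only one of wording. The first half stands: the weekly comparisons can be run as written. It does not rescue the aim, which then has neither the data nor an analysis to answer it.

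Three stronger readings are tempting.

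- A reader might infer that only the early stoppers lack a discharge score. The protocol schedules one for nobody. The early stoppers differ in that even a recent session score is missing. A discharge score added for them alone would mix two timings, in a way that depends on RLAS.
- A reader might infer a definite shrinkage of the difference between arms, with fast recoverers held at about 7 and slow ones at their day-28 level. The documents do not support a figure. They do not state the top of the RLAS (Section 3.4 shows only that it exceeds 7), the length of stay, or how stay relates to recovery. The shrinkage would also arise in a comparison of last study scores, which is not planned. The ceiling argument concerns RLAS; no such loss has been shown for LOCmd, which Hypothesis 2 names.
- A reader might infer that the harm is bias alone and power is untouched. That does not follow: if patients without a score are left out, power falls, as the table shows on assumed shares.

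**Conclusion.** The point holds from the text alone. As written, the trial cannot answer Aim 2: no score at hospital discharge is scheduled in either arm, none can exist in the study data for patients who stop at RLAS 7 or day 28 and remain in hospital, and the analysis listed under the aim concerns within-session change. Missing discharge scores may differ by arm, on the condition that AAT speeds the approach to RLAS 7. The size of the loss is unknown.

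The change should be made, but it does not put the whole trial at risk. The primary outcome, the session-level change in RLAS, needs no discharge score.

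**What to change.** **Preferred.** In Section 3 (Intervention Group item 4 and Control Group item 3) and Section 3.4, keep the present stops for session scoring and add: *for every randomized patient who has not withdrawn consent, including those who stopped at RLAS 7 or day 28, the bedside nurse records RLAS and LOCmd once on the day of hospital discharge.* In Section 4.2, compare that value between arms under Aim 2, and bring the Abstract into line. Patients who die in hospital will have no such score; their handling can be left to the analysis plan.

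The cost is one more bedside score and a protocol change that extends observation to discharge without altering treatment. Section 3 already makes study personnel responsible for seeing that bedside-nurse scores are recorded after a move to another unit.

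**Alternative.** Reword Aim 2 in the Abstract, Section 1.1 and Section 4.2 as status at study exit (first of discharge, RLAS 7 or day 28), analyse the last study score, and make no claim about status at hospital discharge. This costs only wording and an analysis paragraph, but it gives up the discharge question, and the exit score remains limited by the RLAS 7 stop.

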3. STUDY METHODS AND PROCEDURES

All patients admitted to the TICU will have a documented GCS in the medical chart as a part of clinical care. [name] (LH), the study PI, and the Trauma Intensive Care Unit RN subinvestigators will screen the TICU census daily for new patients to identify those admitted with GCS ≤ 8 that meet study criteria. Eligible patients will be followed by the PI or the TICU RNs until the patient is assessed at GCS of 5 or above.

1. Patients with a GCS of 5 or above will be screened for eligibility. Those eligible will be invited to participate and consent will be obtained by study personnel.
2. Consenting subjects will be randomized to the intervention or control arm of the study

3. For patients randomized to the intervention arm, study personnel (PI or TICU RNs) will request a doctor's referral. A referral will be made to LH who will arrange for the patient to receive the intervention with the dog.
4. The control group will be receiving standard of care bedside interventions. During the control measurement period, the only person present will be the bedside nurse who records the measurements.
5. Study personnel will record the RLAS, GCS, Level of Commands, and Movement of Extremities within 24 hours of obtaining consent and order.

Intervention Group

1. When the patient is randomized to the treatment arm, the PI will refer the case to one of the AAC handler/dog teams approved for work on the study for the intervention. The AAC handler will respond within 3 days and will request data measurements be taken by the bedside RN. These measurements will include (see attachments for data collection sheet):
 - A. RLAS Score
 - B. GCS Score
 - C. Level of Command (LOCmd)-0, 1 or 2 or 3-step
 - D. Movement of Extremities
2. Following the recording of the above measurements, the AAC team will provide AAT to the patient.
3. Immediately following the intervention, the same scores will be measured by the same licensed healthcare professional.

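### The window for ΔRLAS is defined differently in the two arms, has no stated length in either, and is not matched, so a difference may partly reflect the window rather than AAT.

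*Protocol*

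**What the plan says.** **AAT arm (Protocol, Section 3, Intervention Group).** The bedside nurse records RLAS, GCS, level of command and movement. Then: "Following the recording of the above measurements, the AAC team will provide AAT to the patient". The second score comes at the end: "Immediately following the intervention, the same scores will be measured by the same licensed healthcare professional". The session is booked, since the text provides for absence: "If the patient is unavailable for AAT at the time of the scheduled intervention". Frequency: "AAT and measurements of the same data will continue up to three times weekly after the initial measurements". No session length is given.

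**Control arm (Section 3, Control Group).** Item 2 puts the period within standard bedside care: "During the control measurement period, the only person present will be the bedside nurse who records the measurements". The scores "will be measured by the same licensed healthcare professional before and after each interaction with the healthcare professional". Item 3 then sets a frequency: "The PI will be responsible for collecting measurements of the same data up to three times weekly after the initial measurements". No length, start, stop or link to an AAT visit is given.

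**Analysis (Section 4.2).** ΔRLAS "will be defined as RLAS during AAT/sham" minus the score before it. Visit-level values are averaged within each of weeks 1 to 4, and the weekly values are compared between arms by Wilcoxon rank sum test. For GCS alone there is a clock rule: chart values from the hour before and the hour after.

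**The concern.** Section 4.2 subtracts the two scores in both arms as if they spanned the same kind of period. Section 3 gives one arm a booked session and the other an ordinary care contact. Arousal after severe brain injury can change within a visit, so the chance of seeing a change depends on how long the patient is observed, when, and what happens meanwhile.

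The window is set by the assigned arm, so randomization cannot balance it. The problem would remain with a perfectly objective rater. If the intervals are not matched at the bedside, no later analysis can make them so. At stake is whether the Aim 1 comparison can be attributed to AAT.

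**Working it through.** The protocol gives no duration, and no figure of its own on this point to reproduce. The check is therefore a comparison of the texts, followed by an illustration on assumed values.

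**1. The two windows side by side**

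| Feature | AAT arm | Control arm |
|---|---|---|
| What is bracketed | Scheduled AAT session | Each interaction with the professional |
| Length | Not stated | Not stated |
| Timing | Booked | Not stated |
| Frequency | Up to three times weekly | Each interaction (item 2); up to three times weekly (item 3) |
| Second score, Section 3 | Immediately after | After |
| Second score, Section 4.2 | During | During |

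Three things need reconciling:
- item 2 with item 3 on how often controls are scored;
- *during* (Section 4.2) with *immediately following* (Section 3) for the second score;
- the *sham* of Section 4.2 with Section 3, which describes none.

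**2. Steady recovery (assumed rates)**

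Shift in ΔRLAS = recovery rate × difference in window length. Assume a gain of 6 levels, over 28 days or over 7 days.
- Slow: 6 / (28 × 24) = 0.009 level per hour. For 30 minutes: 0.0089 × 0.5 = 0.004 level.
- Fast: 6 / (7 × 24) = 0.036 level per hour. For 30 minutes: 0.0357 × 0.5 = 0.018 level.

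Drift alone therefore moves the mean very little.

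**3. Changes of level within the window (assumed rates)**

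Simulation with no AAT effect: 50 patients per arm (Section 4.1), 3 visits in a week, weekly mean per patient, two-sided Wilcoxon test at 0.05 (the level is assumed). The chance of a one-level change in a window of t hours is 1 − exp(−λt). For example, with λ = 0.25 per hour it is 1 − exp(−0.25 × 10/60) = 4.1% in 10 minutes and 1 − exp(−0.25 × 30/60) = 11.8% in 30 minutes.

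Rejection rate when every change is a rise:

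| Control / AAT window (min) | λ = 0.1 | λ = 0.25 | λ = 0.5 |
|---|---|---|---|
| 20 / 20 | 3.9% | 4.7% | 4.7% |
| 10 / 20 | 13% | 28% | 49% |
| 10 / 30 | 34% | 69% | 93% |
| 30 / 10 | 34% | 68% | 92% |

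In the last row the significant results favour control. The direction follows whichever window is longer.

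Changing the mix of rises and falls, for 10 against 20 or 30 minutes and the same λ:
- 75% rises: about 7% to 37%.
- Equal rises and falls: about 4% to 6%.

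With rises only, at the recovery rates of step 2 and 10 against 30 minutes, rejection is below 1% at the slow rate and about 10% to 12% at the fast rate.

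**The case against.** The strongest reply is that the documents do not show unequal windows. A reader might infer that AAT sessions are long, that control contacts are brief and chosen by the nurse, and that control ΔRLAS is thereby held near zero. None of this is stated. A booked session has a set time, not a set length. Nobody is named as choosing the control moment, and item 3 makes the principal investigator responsible for collecting the data. Bedside care could outlast a dog visit, and the bias would then run against AAT. This part of the objection stands in full.

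The mechanism can also be questioned. The assumed λ of 0.1 to 0.5 per hour means 0.1 × 24 = 2.4 to 0.5 × 24 = 12 changes of level a day. That cannot be net recovery on a scale where participation ends at level 7. It fits fluctuation, which runs both ways, and symmetric fluctuation leaves the error rate near nominal. This stands too: material inflation needs mainly upward change within the window and a real gap in length.

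Third, items 2 and 3 can be read together, with item 3 giving the frequency and item 2 the before-and-after pair. Extra control pairs would add no patients, because values are averaged within the week. This is a fair reading, and it may settle the frequency. It settles neither length nor timing.

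Finally, the data collection sheet is not shown and may hold times. Its lack of time fields cannot be asserted. Recorded times would document a mismatch but would not prevent it.

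**Conclusion.** The concern holds as a matter of unspecified and unmatched windows, not of proven unequal ones. The interval that defines the primary outcome depends on the assigned arm, has no stated length in either, and is called a sham in the analysis without any procedure behind it. A difference in ΔRLAS may therefore partly reflect window length, timing or content.

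Direction and size cannot be read from the documents. The bias is small under steady recovery (0.004 to 0.018 level for a 30-minute difference), and the error rate stays near nominal under symmetric fluctuation. It becomes serious only if the windows differ and change within a visit is mainly upward. The 13% to 93% range rests on those two assumptions and on the chosen λ and window lengths.

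The change should still be made: it is cheap, and the fault cannot be repaired after data collection.

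**What to change.** In Section 3, state one planned observation interval for both arms. This means stating the planned AAT session length, which the protocol now leaves open, and using the same length for controls. Fix the same scoring point for the second score in both arms, and reconcile Sections 3 and 4.2 on whether that point falls during or immediately after the session.

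Replace Control Group item 2 with control pairs at pre-booked slots, up to three times weekly as in item 3, at times of day comparable to AAT visits, with standard bedside care in between. Delete the reference to each interaction. In Section 4.2, define the sham as this control window. Make sure that the data sheet records start and stop times in both arms.

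The cost is a wording change in two sections and, if not already present, two time fields. No staff are added. The downside is slightly less flexible timing of control scores. Matched timing does not make the content of the two periods alike. It removes length and time of day as explanations.
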